6.7 Statistical Analysis Plan

As a patient's status in Group A may be changed during the study from waiting for HSCT to being a HSCT recipient, the effect of HSCT will be assessed in a various ways. Our first approach will be using the Mantel-Byer method.⁴⁰ Mantel and Byer (1974) proposed a modified life table to avoid 'time-to-treatment' bias and to accommodate the transient nature of transplant status. The second approach is to treat patient's transplant status as a time-dependent function, $X=X(t)$, as proposed by Crowley and Hu.⁴¹ In this approach, $X(t)$ is an indicator variable at time t , that is, $X(t)=0$ if the patient has not received the transplant at time t , and 1 if the patient has received the transplant at time t . Age at HSCT will be constructed in a similar manner. Another approach is a landmark analysis at one year after study entry.⁴² We will also explore a combination of a pointwise comparison of survival curves at specified time t and a log-rank test after t , using the method proposed by Logan et al.⁴² The last two approaches are particularly suitable as the overall survival between the two groups is not expected to be different during the first year of study, but instead start to separate after approximately one year.

QoL will be assessed using the EORTC-30³⁷ and the QUALMS-1, a disease-specific measure developed by [name] and colleagues at DFCI which is currently undergoing validation.³⁸ The predictability of IPSS or WPSS score on survival outcome will be assessed using the time-dependent ROC curve estimation for censored survival data (survival ROC), proposed by Heagerty et al.⁴⁴⁻⁴⁵ The predictability of these two scoring systems will be compared in each group. In addition, a subset analysis will be performed for Group A (HSCT) to prospectively determine if disease- or patient-related factors predict outcomes of HSCT for MDS in patients aged 60-75. These factors include baseline age at HSCT, IPSS score, WPSS score, number of cytopenias, transfusion dependence, disease duration, prior therapies, and Sorror co-morbidity index. In this subset analysis, standard time-to-event analysis as well as competing risks data analysis⁴⁶ will be performed.

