3.2 Secondary Objectives

1. To prospectively compare the progression-free survival (PFS) of patients in Group A to that of patients in Group B as defined above (**secondary outcome**).
2. To prospectively compare changes in the quality of life (QoL) from baseline to two years of patients in Group A to that of patients in Group B as defined above (**secondary outcome**).

3. To assess the potential association of patient- and disease-specific factors—including International Prognostic Scoring System (IPSS) score, WHO-based Prognostic Scoring System (WPSS) score, number of cytopenias, transfusion dependence, disease duration at baseline, prior therapies and age at HSCT—with the primary and secondary outcomes.

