4.0 STUDY POPULATION

Eligible patients will be 60 to 75 years old with a diagnosis of MDS or related disorder (eg, MDS/MPD or CMML) who have disease that is advanced enough to warrant RIC HSCT (defined by high-risk cytogenetics,³⁴ int-2 or high-risk on IPSS³⁵ or transfusion dependence as defined by WPSS³⁶) and who are physically fit enough to undergo RIC HSCT as assessed by pre-determined measures of organ function. Patients whose baseline donor status is known will be excluded; however, knowledge of HLA status is allowed as long as a donor search has not been performed.

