4.2 Exclusion Criteria

1. Known baseline conversion to AML (eg, $\geq 20\%$ peripheral or marrow blasts).
2. Knowledge of potential donor status at study entry. Of note, knowledge of HLA status WITHOUT a related or unrelated search is allowed.
3. History of prior malignancy within the past year, except for adequately-treated carcinoma in situ of uterine cervix, basal cell or squamous cell skin cancer.
4. Any severe concurrent disease, infection, or comorbidity that, in the judgment of the principal investigator, would make the patient inappropriate for HSCT at the time of study entry.
5. Psychiatric disorders including dementia that would preclude obtaining informed consent or the ability to participate in an ongoing research study.

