6.6 Secondary Outcomes

Secondary outcomes include PFS and changes in self-reported QoL. PFS is defined as time from enrollment until evidence of progression to acute leukemia (time until increase in marrow or peripheral blasts to >20%). QoL will be assessed via changes between baseline and two-year assessments on the EORTC-30 and QUALMS-1. We also plan baseline assessment of IPSS and WPSS, number of cytopenias, transfusion dependence, disease duration at baseline, prior therapies and age at HSCT. Of note, we have not based our power calculations on these outcomes and covariates due to their exploratory nature.

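### None of the four HSCT versus no-HSCT analyses in section 6.7 adjusts for baseline prognosis, so the non-randomised primary comparison can be biased in either direction

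*Combined protocol and SAP*

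**What the plan says.** Section 6.1 describes an observational study whose primary comparison is overall survival (OS) with HSCT (Group A) against no HSCT (Group B). Section 6.7 lists four ways to make it:

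- "Our first approach will be using the Mantel-Byer method";
- a time-dependent indicator X(t), equal to 1 once a patient has been transplanted, with the remark "Age at HSCT will be constructed in a similar manner";
- "Another approach is a landmark analysis at one year after study entry";
- a pointwise comparison of the survival curves at a chosen time, combined with a log-rank test after it.

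The reasons given are time-to-treatment bias, the changing transplant status, and curves expected to separate only after about a year.

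Prognostic factors appear elsewhere. Section 6.6 says "We also plan baseline assessment of IPSS and WPSS, number of cytopenias, transfusion dependence, disease duration at baseline, prior therapies and age at HSCT", and adds that "we have not based our power calculations on these outcomes and covariates due to their exploratory nature". Objective 3 in section 3.2 is "To assess the potential association of patient- and disease-specific factors" with the outcomes. Section 6.7 itself uses IPSS and WPSS in survival ROC curves within each group, and uses the wider list as predictors within Group A.

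The design gives some protection. All patients meet common eligibility criteria, and section 4.0 states "Patients whose baseline donor status is known will be excluded"; section 4.2 repeats this as an exclusion.

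**The concern.** The four analyses answer when the transplant happened and how the curves differ over time. They do not ask whether the transplanted patients had a different outlook at entry.

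That question is open here. Section 4.1 admits patients by four alternative routes (IPSS category, secondary MDS, karyotype, or significant cytopenia), so baseline risk can vary widely. The abstract names rapid progression, as well as lack of a donor, as a reason why enrolled patients will not reach HSCT. Lack of a donor may be close to chance; progression is not.

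Section 2.0 explains that Medicare coverage rests on a comparison with similar patients who are not transplanted. Followed as written, no planned analysis makes the two groups comparable even on the prognostic factors that the study records.

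**Working it through.** **1. The plan's own figure.** Inputs from sections 6.2 and 6.4: 290 patients at 1:2, 60 months of accrual plus 60 of follow-up, one-sided 0.025, and the two stated curves with t in months.

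- S_A(60) = 0.19 + 0.4 × 2^-6 + 0.41 × 2^-3 = 0.2475; S_B(60) = 2^(-60/18) = 0.099. These match the stated 25% and 10%.
- Asymptotic log-rank power is 85.4% (83.6% by simulation with 97 and 193 patients), so the stated 85% reproduces. It is the power of an unadjusted two-group test.

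**2. What each analysis controls.**

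| Analysis | Handles | Baseline factor named |
|---|---|---|
| Mantel-Byar | transplant timing | none |
| X(t) model | transplant timing | none; age at HSCT exists only after transplant |
| One-year landmark | timing, late separation | none |
| Pointwise plus log-rank | late separation | none |

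**3. A plausible prognostic effect.** Section 6.4 gives 5-year OS after HSCT of 51% (RAEB-1) and 28% (RAEB-2): ln(0.28)/ln(0.51) = 1.89. The non-HSCT figures in the same section, as written, are 3% (RAEB-1) and 14% (RAEB-2): ln(0.14)/ln(0.03) = 0.56, the opposite direction. So 1.89 in both groups is an assumption, and 1.5, also assumed, was run beside it.

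**4. Baseline imbalance, no HSCT effect.** Simulation with 290 patients, 117 of them HSCT-bound and transplanted at 4 to 6 months if alive (94 to 98 transplanted), the accrual and follow-up above, median OS 18 months, and 4,000 replicates. Monte Carlo standard error is about 0.25 points at 2.5% and 0.65 at 21%. The adverse factor is present in 50% of the other patients; all imbalances are assumed. Entries are the percentage of studies declaring benefit.

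| Factor in HSCT-bound | 40% | 30% | 20% |
|---|---|---|---|
| Mantel-Byar, HR 1.89 | 6.3 | 13.4 | 21.3 |
| Mantel-Byar, HR 1.5 | 4.7 | 8.7 | 12.2 |
| Landmark, HR 1.89 | 5.8 | 9.9 | 15.4 |
| Landmark, HR 1.5 | 4.7 | 6.9 | 9.3 |

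With no imbalance, Mantel-Byar gives 2.2% and the landmark 2.0%. Stratified Mantel-Byar, the stratified landmark and the adjusted X(t) Cox model give 1.8 to 2.9% throughout. At HR 1.89 the mean unadjusted HSCT hazard ratio is 0.94, 0.89 and 0.85. Repeat runs at HR 1.89 gave 5 to 6%, 12% and 20.5 to 22% for Mantel-Byar.

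**5. Imbalance reversed** (60/70/80% in HSCT-bound, HR 1.89). The mean HSCT hazard ratio becomes 1.07, 1.14 and 1.22. The section 6.4 curves give an average hazard ratio of about 0.68 (log -0.390) and a drift of 1.96 + 1.05 = 3.01. Subtracting ln(1.07) = 0.068, ln(1.14) = 0.131 and ln(1.22) = 0.199 leaves drifts of 2.49, 2.00 and 1.47. Approximate power is then 70%, 52% and 31%.

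**6. Limit of baseline adjustment.** Here progression after enrolment blocks HSCT and multiplies the death hazard by 2 or 3. All inputs are assumed: death hazard 0.025 per month; progression 0.03 per month, doubled by a marker present in 50%; half have a donor; HSCT at 4 to 6 months if alive and not progressed. Without the multiplier, every method gives 2.1 to 2.3%.

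| Percentage declaring benefit | 2-fold | 3-fold |
|---|---|---|
| Mantel-Byar | 10.4 | 22.2 |
| Stratified Mantel-Byar | 10.0 | 19.6 |
| Adjusted X(t) Cox | 9.8 | 19.7 |
| Planned landmark | 6.7 | 10.6 |
| Stratified landmark | 5.8 | 9.0 |

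A repeat run gave 6% and 10% for the stratified landmark.

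**7. Shape of the effect.** The A/B hazard ratio implied by section 6.4 is 0.0419/0.0385 = 1.09 at month 0, 0.88 at month 12 and 0.23 at month 60: far from proportional.

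**8. Enough events.** Averaging the curves over 60 to 120 months of follow-up: 96.7 × (1 - 0.213) = 76 deaths in A and 193.3 × (1 - 0.039) = 186 in B, 262 in total. For an assumed 7 to 12 model terms that is 262/7 = 37 to 262/12 = 22 deaths per term.

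**The case against.** The best defence is that the plan points towards covariate modelling without spelling it out. Objective 3 relates the factors to the primary outcome in all patients. Section 6.6 calls them covariates, and its exploratory remark explains only why power was not based on them. Section 6.7 places a second term beside X(t). That is fair as far as it goes. But association with outcome is not adjustment of the HSCT effect, age at HSCT cannot balance the groups at entry, and the other three analyses have no covariate at all. A set chosen after the data are seen, across four analyses, is what pre-specification should prevent.

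The design controls also stand: common eligibility and "Knowledge of potential donor status at study entry" as an exclusion limit selection at entry. They do not remove it.

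Three stronger readings are tempting, and the documents do not support them:

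- That an adjusted X(t) Cox model should become the main estimate. Step 6 shows it about twice as prone to false benefit as the landmark under 3-fold progression, and step 7 shows that one coefficient would average over very different hazard ratios. Section 6.7 itself regards the landmark and the pointwise approach as well suited to late separation.
- That a reversed imbalance would hide a true benefit. Step 5 shows attenuation, severe only at the most extreme imbalance assumed.
- That no survival difference could ever be credited to HSCT. Residual confounding belongs to any observational design and survives the fix; the omission concerns the measured part.

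**Conclusion.** The concern holds. Section 6.7 leaves measured baseline confounding uncorrected in all four HSCT comparisons, although the data to correct most of it are already planned.

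The size cannot be derived from the documents. On assumed imbalances of 10, 20 and 30 points in one factor with hazard ratio 1.5 to 1.89, the false-benefit rate of unadjusted Mantel-Byar is about 5 to 6%, 9 to 13% and 12 to 22%, against a nominal 2.5%. Adjustment or stratification on that factor brings it back to about 2.5%. If sicker patients are the ones transplanted, a real benefit is attenuated instead.

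A reader might infer that the trial's own sources establish a 1.89-fold effect, or that the bias favours HSCT. Neither follows: the non-HSCT subtype figures in section 6.4 run the other way as written, and no passage gives the actual imbalance. Nor does baseline adjustment deal with progression after enrolment.

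**What to change.** Keep the four planned approaches and their order, and add to section 6.7 one baseline set, common to all patients and fixed before any comparison of the groups is seen:

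- Age at enrolment, IPSS or WPSS, cytopenia count, transfusion dependence, disease duration and prior treatment. Add ECOG status and comorbidity only if captured in both groups: ECOG now appears only as an eligibility item and the comorbidity index only for Group A.
- Enter the set as covariates in the X(t) model and in the one-year landmark model. Use a baseline risk stratum in Mantel-Byar and in the log-rank test after the chosen time.
- Do not make a single-coefficient X(t) Cox model the sole main estimate. Where the X(t) model is used, let the HSCT effect vary with time.
- State that adjustment removes only measured baseline confounding, that confounding by later progression remains, and that the landmark describes only patients alive at one year.
- Optional sensitivity analysis: OS by donor versus no donor regardless of HSCT receipt, using the donor status to be captured under section 5.1, with unknown status reported separately.

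The cost is SAP wording and modest analysis time. Age is already an eligibility item and the other core factors are planned at baseline. Some precision is lost: in the illustration at HR 1.89 the standard error of the HSCT log hazard ratio rises from 0.136 to 0.138, 0.136 to 0.139 and 0.135 to 0.142, about 1 to 5%. The SAP should say that the 85% power in section 6.4 applies to the unadjusted log-rank test only.

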1.0 ABSTRACT

Although hematopoietic stem cell transplantation (HSCT) is the only therapy that can cure patients with the myelodysplastic syndrome (MDS), and HSCT has long been the standard of care for younger patients with high-risk disease, the procedure has been traditionally withheld from older patients due to concerns about excessive toxicity and limited underlying overall survival. More recently, however, HSCT with reduced-intensity conditioning (RIC) has been increasingly offered to older patients with the syndrome, a clinical picture that is complicated by the introduction of non-HSCT disease-modifying treatments for MDS such as the DNA methyltransferase inhibitors. We propose an observational study enrolling high-risk MDS patients who are fit enough to undergo RIC HSCT but whose HLA and donor status is unknown at baseline. Whether or not enrollees eventually go on to HSCT—indeed, many will not, due to factors such as lack of a suitable donor or rapid progression of disease—all will be followed for outcomes such as overall survival, progression free survival, and quality of life. Our protocol will generate much-needed comparative outcomes data for older patients with high-risk MDS, and has the potential to greatly influence how the disorder is treated in the United States.

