3.0 STUDY OBJECTIVES

3.1 Primary Objective

To prospectively compare the overall survival (OS) of patients aged 60-75 who undergo HSCT for MDS (Group A) to that of patients aged 60-75 who do not undergo HSCT (Group B) but who have disease of sufficiently high enough risk to warrant HSCT and who are also fit enough to undergo the procedure (**primary outcome**).

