6.4 Primary Outcome

The primary endpoint of this study is 5-year OS. OS is defined as time from study entry to death from any cause. Alessandro et al³⁹ recently reported the impact of WPSS on the outcome of MDS patients who underwent allogeneic HSCT. According to their report, the 5-year OS after HSCT was 51% in RAEB-1 and 28% in RAEB2 with an indication of plateau after 5-6 years post transplant. This observation resembles our experience at DFCI with RIC HSCT for older patients with MDS. Malcovati et al³⁶ reported that 5-year OS was 3% in the RAEB-1 group and 14% in the RAEB-2 group among 426 MDS patients who did not undergo HSCT. Most of the patients in these studies, however, were treated prior to the wide use of DNA-methyltransferase inhibitors. Thus, extrapolating this information and based on our experience at DFCI, we hypothesize that a small portion of patients will be cured with HSCT from the underlying disease and the 5-year OS will be 25%, whereas the 5-year OS will be 10% for the non-HSCT patients and the survival distribution of these patients will follow an exponential distribution. In addition, we expect that there will be an approximately 4-6 month wait time for patients in Group A from enrollment to actual RIC HSCT, thus no difference in OS between the two groups is expected for some period after the start of the study. Based on this information and assumptions, we propose an alternative hypothesis as: $H_a: S_A > S_B$, where S_A denotes the survival distribution of Group A and S_B denotes the survival distribution of Group B. Specifically:

$$S_A = 0.19 + 0.4 \cdot \exp(-t \cdot (\log(2)/10)) + 0.41 \cdot \exp(-t \cdot (\log(2)/20)); \text{ and } S_B = \exp(-t \cdot (\log(2)/18)).$$

The figure depicts these two survival distributions graphically. With this design, 290 patients

will be required to achieve 85% power with one-sided significance level of 0.025. This power calculation is calculated using the R program *Powgrnk* (developed by [name] at DFCI), which computes power of the two-group log-rank test for arbitrary failure time distributions.

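### The IPSS/WPSS survival ROC within Group B selects on later HSCT: early mortality is overstated, and the AUC shifts at early horizons if HSCT uptake depends on the score

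*Combined protocol and SAP*

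**What the plan says.** Section 3.1 defines Group B by the absence of a later event: "patients aged 60-75 who do not undergo HSCT (Group B"). Section 6.1 defines the groups in the same way. Sections 4.0 and 4.2 exclude patients whose donor status is already known, so membership is settled only after enrolment.

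Section 6.4 fixes the clock: "OS is defined as time from study entry to death from any cause". It also expects that "there will be an approximately 4-6 month wait time for patients in Group A from enrollment to actual RIC HSCT".

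Section 6.7 recognises time-to-treatment bias. It lists the Mantel-Byar method, a time-dependent transplant indicator, a one-year landmark and a late-difference comparison, all as ways to assess the effect of HSCT. For the prognostic scores it says only that their predictive value "will be assessed using the time-dependent ROC curve estimation for censored survival data (survival ROC"), and then: "The predictability of these two scoring systems will be compared in each group". For this analysis it gives no landmark, no censoring at HSCT, no weighting and no time horizon.

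The abstract says of HSCT that "many will not, due to factors such as lack of a suitable donor or rapid progression of disease". Section 6.7 also says that the status of a Group A patient "may be changed during the study from waiting for HSCT to being a HSCT recipient".

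**The concern.** Read with sections 3.1 and 6.1, the Group B ROC conditions on the future. A patient who dies in month 3 while a donor is sought counts in Group B as an early death. A patient with the same score who lives to month 5 and is transplanted leaves Group B, and the five months survived without HSCT leave too. Group B is therefore enriched for early deaths relative to the enrolled cohort without HSCT. Group A has the mirror-image problem: with the clock at study entry, every member is certain to survive the wait.

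Two outputs could be affected. Mortality by score level in Group B would be too high at early times. The AUC would also shift if uptake of HSCT varies with the baseline score, because survivors would then be removed at different rates at different score levels.

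**Working it through.** **Plan's own figures.** Section 6.4 gives S_A(60) = 0.19 + 0.4·2^(−6) + 0.41·2^(−3) = 0.2475 and S_B(60) = 2^(−60/18) = 0.099, which match the stated 25% and 10%. Numerical integration of the log-rank test (290 patients, 1:2, 5 years' accrual plus 5 years' follow-up, one-sided 0.025) gives 85.4% power against the stated 85%. The plan states no figure for the ROC analysis.

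**Step 1: mortality in never-transplanted patients.**

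Inputs from the plan:
- survival without HSCT S(t) = 2^(−t/18) (6.4)
- one third of enrollees transplanted (1:2 split, 6.2)
- HSCT at w = 4, 5 or 6 months (6.4)

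Assumption: among patients alive at w, uptake is unrelated to prognosis.

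Uptake among those alive at w is p = (1/3)/S(w). For t ≥ w, survival in Group B is S(t)(1 − p)/(2/3). Deaths before w make up (1 − S(w))/(2/3) of Group B.

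For w = 5: S(5) = 0.825 and p = 0.404. Group B survival at 12 months is 0.630 × 0.596/0.667 = 0.563, so mortality is 43.7%.

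| | No HSCT, whole cohort | Group B, w = 4 | w = 5 | w = 6 |
|---|---|---|---|---|
| Deaths before w, share of Group B | – | 21% | 26% | 31% |
| 6-month mortality | 20.6% | 27.2% | 29.1% | 30.9% |
| 12-month mortality | 37.0% | 42.2% | 43.7% | 45.2% |
| 24-month mortality | 60.3% | 63.6% | 64.5% | 65.5% |
| 60-month mortality | 90.1% | 90.9% | 91.1% | 91.4% |
| Median (months) | 18 | 15.7 | 15.1 | 14.4 |

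**Step 2: AUC.** The plan gives no score distribution, hazard ratio or uptake by score, so these are assumptions:
- three score levels with shares π = 30/40/30%
- medians without HSCT of 28/18/11 months
- HSCT uniformly at 4-6 months
- uptake u among those alive then of 25/40/55% (rising), 40% throughout (equal) or 55/40/25% (falling), so that about one third are transplanted

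For level k in Group B, the survivors at t are n_k = π_k S_k(t)(1 − u_k). The deaths are c_k = π_k(1 − u_k·mean S_k(w)) − n_k. The AUC is Σ c_k(Σ_{j<k} n_j + n_k/2) / (Σc·Σn).

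At 12 months with rising uptake, n = 0.167, 0.151, 0.063 and c = 0.067, 0.117, 0.116. The AUC is 0.0746/(0.2996 × 0.3817) = 0.652. The whole cohort without HSCT gives 0.621.

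| Horizon | True AUC without HSCT | Group B, rising uptake | Equal | Falling |
|---|---|---|---|---|
| 6 months | 0.609 | 0.654 | 0.609 | 0.563 |
| 12 months | 0.621 | 0.652 | 0.624 | 0.593 |
| 24 months | 0.646 | 0.665 | 0.651 | 0.632 |
| 60 months | 0.711 | 0.713 | 0.718 | 0.717 |

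**Step 3: steeper assumptions.** Take a four-level score with hazard ratio 2.0 per level and log-odds of uptake from −1 to +1 per level. The 12-month AUC in Group B then runs from 0.692 to 0.801 against a true 0.746, and is 0.752 with unrelated uptake. At 60 months it runs from 0.806 to 0.848 against 0.826. With hazard ratio 1.5 the 12-month range is 0.592 to 0.715 against 0.654.

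**Step 4: the remedy.** In the hazard-ratio-2.0 setting, take all enrollees from entry, censor at HSCT and estimate survival within score level. The 12-month AUC is then 0.746-0.747 (true 0.746) and survival 0.610-0.611 (true 0.611) for log-odds −1, 0 and +1.

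**The case against.** The plan does not name accuracy without HSCT as the target of the Group B curve. That is the natural reading, but it is a reading. A ROC measures discrimination, so the overstated mortality in Step 1 is not itself an output the sentence promises, and with unrelated uptake the AUC is close to right. The uptake gradient is assumed. The abstract gives lack of a donor and rapid progression as reasons for missing HSCT, and neither supplies a gradient by baseline score. These objections stand, and they limit the size of the point.

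The planned contrast is between two scores in the same patients. In a simulation of two correlated scores with uptake depending equally on both, the difference between their AUCs in Group B was unchanged: 0.015 at 6 months, and 0.017-0.018 against 0.017 at 12 months. It shifted, by about 0.02 at 6 months, only when uptake followed one score and not the other. With about 193 patients in Group B (two thirds of 290), the sampling standard deviation of the AUC is about 0.041 at 6 months and 0.037 at 12, so the shift is about the size of the noise.

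Sections 6.4 and 6.7 also speak of Group A patients who are still waiting. If deaths during the wait were counted in Group A, the bias in Group B would differ. Sections 3.1 and 6.1 point to actual receipt, so the texts need reconciling.

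A reader might infer that this undermines a headline product of the study, because section 8.0 promises evidence on the usefulness of the scores. That passage concerns outcomes of transplantation and does not support a claim about Group B. A reader might also infer that risk is always overstated or that the AUC is biased in a known direction. Neither follows. With hazard ratio 2.0 and log-odds +1, 60-month survival in Group B is 21.4% against a true 18.5%.

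**Conclusion.** The point holds as a limited one. As written, the Group B ROC selects on a later event, and no method in section 6.7 is applied to prevent it. On the plan's inputs, with uptake unrelated to prognosis, the mortality excess in Group B is about 5 to 8 points at 12 months and about 1 point at 5 years.

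The effect on the AUC is conditional. It is under 0.01 at 12 months when uptake is unrelated to the score. Under the assumed three-level gradients it is about 0.03-0.05 in either direction at 6-12 months, about 0.02 at 24 months and under 0.01 at 5 years. The steeper four-level assumptions widen this to about 0.06 at 12 months and 0.02 at 5 years. The IPSS-WPSS contrast is affected less, to the extent that both scores relate to uptake alike.

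Section 6.6 calls the secondary outcomes and covariates exploratory and bases no power on them, and the primary comparison is untouched. This is a worthwhile improvement, not a threat to the study.

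**What to change.** - For ROC curves without HSCT, include all enrollees from study entry and censor at HSCT. Use inverse-probability-of-censoring weights built on the baseline score and the other recorded prognostic covariates (section 6.6 lists cytopenias, transfusion dependence, disease duration and prior therapies). A landmark ROC that classifies patients by HSCT status at the landmark is an acceptable alternative.
- For Group A, start the ROC clock at HSCT, and say that this origin differs from the OS definition in section 6.4.
- State the ROC horizon or horizons.
- Reconcile sections 3.1 and 6.1 with the references in sections 6.4 and 6.7 to Group A patients still waiting, so that a patient who dies before HSCT has one defined place.

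The cost is modest extra analysis work. The baseline scores, donor status and outcomes are already to be collected (section 5.1). Residual bias remains if progression after entry drives uptake beyond what the recorded covariates capture. The abstract's mention of rapid progression makes that plausible, so weights on the score alone would not be enough.

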5.0 STUDY DESIGN AND METHODS

5.1 Data Collection

Data for this study will be collected using the existing mechanisms of the Dana-Farber/Harvard Cancer Center (DF/HCC) Leukemia Clinical Research Information Systems (Leukemia CRIS) for baseline data (all study participants). For patients who do not go on to HSCT, Leukemia CRIS will be used to collect their outcomes, while HSCT patients will have outcomes collected in the Center for International Blood and Marrow Transplant Research Stem Cell Therapeutic Outcomes Database (CIBMTR SCTOD). Leukemia CRIS is a state-of-the-art information infrastructure for hematologic oncology at the DF/HCC, developed to link clinical outcomes to blood and tissue samples, and to lay the foundation for innovative pilot studies and health services research. The database has been accruing data since January of 2006. Patients in Leukemia CRIS have baseline information and a new patient survey entered at 3 months; they are then assessed for outcomes every 6 months for 3 years. After 3 years, their records are updated for outcomes once per year. Note that baseline IPSS, WPSS and entry criterion (eg, histology, cytogenetics, or transfusion requirements), or as well as eventual HLA status and donor status will be added to Leukemia CRIS data screens and captured for MDS-TAO patients. Also, QoL will be assessed at baseline and two years with the EORTC-30,³⁷ a validated quality of life instrument, as well as the QUALMS-1, an MDS-specific quality of life instrument being validated by [name] under OHRS protocol 13-346.

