8.0 POTENTIAL CLINICAL AND POLICY IMPACT

To our knowledge, our planned analysis will be the first large study of comparative outcomes associated with RIC HSCT versus non-HSCT for older patients with MDS—crucial information for our health care system as our country becomes increasingly concerned with the costs of health care and comparative effectiveness. Our results will provide essential insight to patients and practicing oncologists regarding the advisability of HSCT for MDS patients in this largely understudied age group, as well as help policymakers and funding sources such as CMS understand if the procedures truly lead to improved outcomes. Next, the data we plan to collect regarding potential changes in quality of life associated with HSCT in this age group promise to address an important gap in the current HSCT literature. Finally, MDS-TAO would also provide a long-overdue source of primary and prospective data for MDS researchers as to the usefulness of the IPSS and WPSS in prognosticating for transplantation-related outcomes.

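### Objective 3 relates seven factors to outcome without restricting them to HSCT recipients, but section 6.7 analyses four of them only in Group A, which holds about 29% of the expected deaths

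*Combined protocol and SAP*

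**What the plan says.** Section 3.2, objective 3, is "To assess the potential association of patient- and disease-specific factors", and its list of seven factors ends "prior therapies and age at HSCT—with the primary and secondary outcomes". Objectives 3.1 and 3.2 (items 1 and 2) define those outcomes (OS, PFS, change in QoL) as comparisons of Group A with Group B.

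Section 6.7 covers the seven factors in three ways:

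- **IPSS and WPSS:** time-dependent ROC curves for survival. "The predictability of these two scoring systems will be compared in each group".
- **Age at HSCT:** alongside the transplant indicator X(t), "Age at HSCT will be constructed in a similar manner".
- **All seven, plus a co-morbidity index:** "a subset analysis will be performed for Group A (HSCT) to prospectively determine if disease- or patient-related factors predict outcomes of HSCT". "These factors include baseline age at HSCT, IPSS score, WPSS score, number of cytopenias, transfusion dependence, disease duration, prior therapies, and Sorror co-morbidity index".

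Section 5.1 adds "baseline IPSS, WPSS and entry criterion" to the data captured for study patients. Section 6.6 plans baseline assessment of the objective 3 factors and calls these outcomes and covariates exploratory, with no power calculation based on them.

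**The concern.** The objective's population and that of the analysis differ for four of the seven factors. Group B is expected to be twice the size of Group A, and its data on those four factors would be collected but have no stated use.

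Two things follow:

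- **Precision.** Leaving out Group B discards most of the information on how these factors relate to survival.
- **Interpretation.** A factor that shortens survival after HSCT may shorten it equally, or more, without HSCT. A fit among recipients alone cannot tell a generally poor prognosis from a smaller effect of HSCT. Recipients are also selected after enrollment. The abstract says many enrollees will not reach HSCT, for reasons that include rapid progression, so an association among recipients need not describe all enrollees.

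Section 8.0 says the results will inform patients and oncologists "regarding the advisability of HSCT for MDS patients in this largely understudied age group". If factor results are to inform that question, they need the non-HSCT comparison.

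**Working it through.** **Step 1. Where each factor is analysed in 6.7**

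- IPSS, WPSS: both groups (survival ROC) and the Group A subset.
- Age at HSCT: time-dependent term and the Group A subset. It exists only for transplanted patients.
- Number of cytopenias, transfusion dependence, disease duration, prior therapies: the Group A subset only.

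So four of seven have no stated Group B analysis, and no factor-by-HSCT term appears anywhere.

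**Step 2. Inputs**

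- 290 patients at 1:2 (6.2), taken as 97 and 193.
- 60 months of accrual and 60 months of further follow-up (6.2).
- Survival curves from 6.4, t in months: S_A = 0.19 + 0.4·2^(−t/10) + 0.41·2^(−t/20); S_B = 2^(−t/18).
- Assumptions: uniform accrual, no dropout.

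**Step 3. Reproduce the plan's own figure**

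The curves give 24.75% and 9.9% at 60 months, matching the stated 25% and 10%. Large-sample log-rank power at one-sided 0.025 is 85.4% (83.4% in 10,000 simulated trials), against the stated 85%. The design is therefore read as intended.

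**Step 4. Expected deaths**

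Follow-up per patient runs uniformly from 60 to 120 months, so expected deaths are N × (1 − mean of S over 60 to 120 months).

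- Group A: mean S = 0.19 + 0.4 × (14.427/60) × (2^−6 − 2^−12) + 0.41 × (28.854/60) × (2^−3 − 2^−6) = 0.19 + 0.0015 + 0.0216 = 0.2130. Deaths = 97 × 0.7870 = 76.3.
- Group B: mean S = (25.969/60) × (0.0992 − 0.0098) = 0.0387. Deaths = 193 × 0.9613 = 185.5.
- Group A share = 76.3/261.9 = 29%.

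The share is stable at 1:2. It is 29.5% from 5-year OS alone (72.75 of 246.45), 29.9% with 24 months of further follow-up, and 30.9% with none. At 1:1 it would be 45% (114.1 of 253.5).

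**Step 5. Precision of a factor's hazard ratio**

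The documents give no factor prevalences. Assume a binary factor in 50% of patients, so SE(log HR) ≈ 2/√deaths.

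- Group A alone: 2/√76.3 = 0.229; exp(1.96 × 0.229) = 1.57.
- All patients, one common effect: 2/√261.9 = 0.124; exp(1.96 × 0.124) = 1.27.

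The smallest hazard ratio detectable with 80% power (two-sided 0.05) is exp(2.8016/√(0.25 × deaths)): 1.90 from Group A and 1.41 from all patients. At 25% prevalence (0.1875 in place of 0.25) these are 2.10 and 1.49.

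**Step 6. Precision of a factor-by-HSCT term**

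- Groups treated as fixed: SE = √(4/76.3 + 4/185.5) = 0.272; exp(1.96 × 0.272) = 1.70.
- With X(t), Group A deaths before HSCT count as untransplanted. Section 6.4 expects a wait of 4 to 6 months. S_A(4) = 0.850 and S_A(6) = 0.787, so 97 × 0.150 = 14.5 to 97 × 0.213 = 20.7 deaths move across.
  - At 4 months: √(4/61.8 + 4/200.0) = 0.291, giving 1.77.
  - At 6 months: √(4/55.6 + 4/206.2) = 0.302, giving 1.81.

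**The case against.** The best defence is that objective 3 asks for association and not for who benefits, so the absence of an interaction term contradicts nothing. That stands. A reader might infer that the plan fails an objective to identify who gains from HSCT, but no such objective is stated. The missing term limits what the factor results can show.

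Section 8.0 also gives limited support to the stronger reading. Its remark on advisability fits the overall comparison of the two groups, and the same section names prognosis for transplantation-related outcomes as an aim, which the Group A analysis serves.

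A reader might also conclude that the objective goes unanswered for the two thirds of enrollees in Group B. It does not: IPSS and WPSS are assessed for survival in each group. The gap is four factors.

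Two further arguments are not supported. Too few deaths per parameter in Group A, and redundancy between WPSS and transfusion dependence, both presuppose one joint model of all eight factors. Section 6.7 specifies no such model, and the documents do not list the components of WPSS.

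The gain to 1.27 holds only if the factor acts alike with and without HSCT. It does not carry over to group-specific effects once an interaction is included.

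Finally, section 6.6 labels these covariates exploratory. That excuses low power, but it does not explain leaving Group B out when the baseline assessments are already planned.

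**Conclusion.** The point holds as a gap between a stated objective and the stated analysis. Objective 3 is not restricted to recipients, yet four of its seven factors are analysed only in Group A, on about 76 of 262 expected deaths (29%). What that analysis yields is prognosis after HSCT. It gives no Group B association for those four factors and no estimate of whether the HSCT effect varies with them.

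The death counts rest on the 6.4 curves, the 1:2 split, uniform accrual and no dropout. The precision figures add an assumed 50% prevalence and, for 1.27, a common effect. The fixed-group interaction limit of 1.70 is optimistic, and 1.77 to 1.81 is more realistic under X(t).

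The primary comparison and its 85% power are untouched. The change should be made before analysis, but the study does not depend on it.

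**What to change.** In section 6.7:

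1. Add the baseline factors already planned for enrollees (5.1 and 6.6) to the time-dependent X(t) model, fitted as a Cox regression in all 290 patients, and report their main-effect associations with OS.
2. Add factor-by-X(t) terms one factor at a time, labelled exploratory. Report the HSCT hazard ratio at each factor level with its interval, and state in advance that limits of about 1.7 to 1.8 either way are expected.
3. Keep the Group A time-to-event and competing-risks analysis for prognosis after HSCT, including age at HSCT and the co-morbidity index. That index is not in the 6.6 baseline list, so it belongs here unless it is also to be collected in Group B.

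If recipients only was the intention for the four factors, objective 3 should say so.

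The cost is SAP wording and modest programming, with no extra patients and no new data for the objective 3 factors. The drawback is imprecise interaction estimates: with groups treated as fixed and a 50/50 factor, only a ratio of hazard ratios of about exp(2.8016 × 0.272) = 2.1 would be detected with 80% power. A null interaction should therefore not be read as evidence that the HSCT effect is uniform.
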